4.1. Primary Objective

The primary objective of this study is to characterize both the TTP distributions and the effect on TGF- β -associated serum biomarkers (for example, TGF- β , AFP, E-cadherin) of study treatment in patients with HCC.

4.2. Secondary Objectives

The secondary objectives of the study are as follows:

- To evaluate the safety of LY2157299 as monotherapy and in combination with sorafenib in HCC patients
- To evaluate the population pharmacokinetics (PK) of LY2157299 as monotherapy and in combination with sorafenib
- To recommend which doses of LY2157299 as monotherapy and in combination with sorafenib to use in future trials recruiting HCC patients
- To characterize other time-to-event distributions, such as progression-free survival (PFS, based on Response Evaluation Criteria in Solid Tumors [RECIST] 1.1 and modified RECIST [mRECIST], for HCC) and overall survival (OS)
- To estimate antitumor efficacy using response rate (RR, based on RECIST 1.1 and mRECIST, for HCC)
- To assess patient-reported outcome (PRO) measures of disease-specific symptoms and health-related quality of life (Functional Assessment of Cancer Therapy Hepatobiliary [FACT-Hep])
- To explore E-cadherin, pSMAD, and β -integrin (and other markers associated with epithelial-to-mesenchymal transition (EMT) transformation and the TGF- β -associated signaling pathway) presence in the original diagnostic tumor tissue and optional posttreatment tumor tissue and the correlation of this with both clinical efficacy endpoints and biomarker response
- To explore the utility of exploratory imaging techniques (for example, positron emission tomography [PET] scan, contrast echography) to assess treatment effect with LY2157299 as monotherapy and in combination with sorafenib when possible
- To explore fibrosis-related biomarkers, such as Fibrotest

5. A Priori Statistical Methods

5.1. Endpoint Definitions

5.1.1. Clinical Efficacy Endpoints

The primary efficacy endpoint for this study is time to tumor progression (TTP). Secondary efficacy endpoints include progression-free survival (PFS), overall survival (OS), duration of tumor response (DR), time to treatment failure (TTF), overall response rate (ORR) and clinical benefit rate.

A central review of all radiographic examinations will be conducted. Response will be determined by both RECIST 1.1 and mRECIST; although, the primary method will be RECIST 1.1. Best response is determined from the sequence of cycle responses assessed. For complete response (CR) or partial response (PR), best response must be confirmed. A second assessment should be performed ≥ 28 days but no longer than 42 days after the first documentation of response. Two objective status determinations of CR before progression are required for a best response of CR. Two determinations of PR or better before progression, but not qualifying for a CR, are required for a best response of PR. All lesions must be assessed by the same method as at baseline to qualify for response.

All patients will be followed for progression and OS. Patients who come off therapy due to objective progressive disease will be followed for survival every 2 months. From Amendment (b), patients that are clinically asymptomatic may continue on study treatment even if they have objective progression. These patients will then be discontinued from study treatment because of overall symptomatic deterioration, worsening of biomarker results, or other causes. The date of objective progression and date of overall symptomatic deterioration will be collected on CRF. The time to tumor progression, progression free survival, and response rate will be estimated up to the date of objective progressive disease.

Patients who come off therapy and do not have objective progressive disease should be followed every 2 months after discontinuation from study treatment until objective progressive disease is determined (using the same radiological scans as at baseline) or death. Patients who progress should then be followed for survival every 2 months, even if a patient starts a new anticancer therapy. The start date of any new anticancer therapy (occurring during the 30-day poststudy drug discontinuation period or during the long-term follow-up period) will be collected.

The definitions for efficacy endpoints are as follows:

- **Time to tumor progression (TTP)** is measured from the date of first dose to the first date of objective progression of disease. For each patient who is not known to have had a progression of disease as of the data-inclusion cut-off date for a particular analysis, or who has died without progression of disease, time to progression will be censored for that analysis at the date of the patient's last tumor assessment prior to that cut-off date.
- **Progression-free survival (PFS)** duration is measured from the date of first dose to the first date of objective progression of disease or death from any cause. For each patient who is not known to have died or to have had a progression of disease as of the data-inclusion cut-off date for a particular analysis, PFS will be censored at the date of last prior contact. PFS duration will be calculated and analyzed twice: (1) including clinical

progressions of disease (i.e. not based on lesion measurements), and (2) excluding clinical progressions.

- **Overall survival (OS)** duration is measured from the date of first dose to the date of death from any cause. For each patient who is not known to have died as of the data-inclusion cut-off date for a particular analysis, OS duration will be censored for that analysis at the date of last prior contact. Patients that are still alive when the study finished will be censored at the end of the study.
- **Duration of tumor response (DR)** is measured from the date of the first objective status assessment of a CR or PR to the first date of objective progression of disease or death from any cause. For each patient who is not known to have died or to have had a progression of disease as of the data-inclusion cut-off date for a particular analysis, duration of tumor response will be censored at the date of last prior contact.
- **Time to treatment failure (TTF)** is measured from the date of first dose until the date of discontinuation of study treatment due to AE, progression of disease, or death from any cause. For each patient who has discontinued study treatment for any other reason, time to treatment failure will be censored at the date of discontinuation of study treatment. If a patient is still on study treatment as of the data-inclusion cut-off date for the particular analysis, time to treatment failure will be censored for that patient at that cut-off date.
- **Overall response rate (ORR)** is the percentage of patients who achieved a best overall response of either complete response (CR) or partial response (PR). The overall response rate for each dose cohort will be estimated by dividing the total number of confirmed responders by the number of patients who received at least 1 dose of study drug.
- **Clinical benefit rate** is the percentage of patients who received benefit of a confirmed response, PR, or SD per RECIST 1.1 and mRECIST. The clinical benefit rate for each dose cohort will be estimated by dividing the total number of patients experiencing benefit by the number of patients who received at least 1 dose of study drug.

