At the time all parts of the study are considered complete, the study will be considered complete and those patients still on treatment may enter the treatment extension period and continue to receive the study treatment (see Section 7.1.1).

All patients will be followed for OS until study completion.

End of study (trial) is the date of the last visit or last scheduled procedure shown in the Study Schedule for the last active subject in the study (this includes all patients who enter the extension period). The European Union (EU) has additional reporting requirements associated with the end of study. Consult regional standard operating procedures (SOPs) for further information.

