7.1.1. Extension Period

After study completion (i.e., study objectives met, see Section 7.1), all patients who are on study treatment (LY2157299 alone or LY2157299 with sorafenib in Part C, LY2157299 with ramucirumab in Part D, or LY2157299 alone in Part E) and who are eligible for the extension period may continue to receive study treatment until one of the criteria for treatment discontinuation is met (Section 8.3.1). Patients who are no longer on study treatment at the time of study completion and who have completed at least the 30-day follow-up visit (V801) will be discontinued from long-term follow-up and therefore reach the end of the study, unless they are being followed due to unresolved safety concerns. Lilly will notify investigators when the extension period begins.

During the extension period, all AEs and study drug exposure will be reported on the case report form (CRF). SAEs will also be reported on the CRF and to Lilly Global Patient Safety (see Section 10.2.1.1). In the event that an SAE occurs, Lilly may request additional information (such as local laboratory results, concomitant medications, and hospitalizations) in order to evaluate the reported SAE.

All patients in the extension period will be treated following the Study Schedule (see [Attachment 1](#)). This will ensure that appropriate risk/benefit assessments are conducted for all patients.

The patient's participation in the extension period will end after study drug(s) is discontinued. The date and reason for treatment discontinuation will be collected on the CRF. Data will be collected until 30 days after the patient has been discontinued from study treatment and at this point, the patient will have ended the study. If the patient dies within the 30-day follow-up period, the reason for study discontinuation will be "Death", and the cause and date of death recorded. Otherwise, the reason for study discontinuation will be noted as "Completed". There will be no long-term post-discontinuation follow-up period for these patients, unless any safety concerns have not resolved. Requests for updates on survival may occur.

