12.2.2. Definition of Clinical Efficacy Measures

Anticancer therapy is considered any treatment after failure or discontinuation on LY2157299.

Best response is determined from the sequence of cycle responses assessed. For complete response (CR) or partial response (PR), best response must be confirmed. A second assessment should be performed ≥ 28 days after the first documentation of response. Two objective status determinations of CR before progression are required for a best response of CR. Two determinations of PR or better before progression, but not qualifying for a CR, are required for a best response of PR. Best response of stable disease (SD) is defined as disease that does not meet the criteria for CR, PR, or progressive disease and has been evaluated at least 1 time, at least 6 weeks after start of study treatment.

Evidence of progression is as defined in the RECIST 1.1 criteria (primary method) and mRECIST for both determining clinical response and time-to-event endpoints except for OS.

The following definitions for time-to-event measures will apply:

- OS duration is measured from the date of randomization to the date of death from any cause. For each patient who is not known to have died as of the data-inclusion cut-off date for a particular analysis, OS duration will be censored for that analysis at the date of last prior contact.

- PFS duration is measured from the date of randomization to the first date of progression of disease or of death from any cause. For each patient who is not known to have died or to have had a progression of disease as of the data-inclusion cut-off date for a particular analysis, PFS will be censored at the date of last prior contact. PFS duration will be calculated and analyzed twice: (1) including clinical progressions of disease not based on lesion measurements, and (2) excluding clinical progressions.

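### The SAP adds an end-of-study censoring sentence for OS that conflicts with the last-contact rule it shares with the protocol; read as a study-level date, it can only push OS upward

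*SAP*

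**What the plan says.** Protocol 12.2.2 has one OS censoring rule. For a patient not known to have died by the data cut-off, "OS duration will be censored for that analysis at the date of last prior contact". SAP 5.1.1 repeats that rule and follows it with a sentence the protocol does not have: "Patients that are still alive when the study finished will be censored at the end of the study". In the same SAP section, PFS and duration of response use last contact alone.

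The SAP does not define when the study has finished. The documents offer three candidate dates:

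- **Study completion.** SAP 5.3.1 ties this to 85% of the Part C survival events. Protocol 7.1 ties it to all parts being complete, and says "All patients will be followed for OS until study completion".
- **Trial-level end of study.** Protocol 7.1: "End of study (trial) is the date of the last visit or last scheduled procedure shown in the Study Schedule for the last active subject". The definition extends to patients in the extension period.
- **The patient's own exit.** Protocol 7.1.1 says that off-treatment patients, at study completion, "will be discontinued from long-term follow-up and therefore reach the end of the study, unless they are being followed due to unresolved safety concerns".

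For patients in the extension period, Protocol 7.1.1 collects data until 30 days after treatment stops and then says: "There will be no long-term post-discontinuation follow-up period for these patients", unless a safety concern is unresolved.

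**The concern.** A patient with no recorded death can fall under both SAP sentences, and they can give different dates. On either study-level reading, the second date can lie after the last time anyone knew the patient was alive. Survival contacts are about 60 days apart, and at study completion off-treatment patients leave long-term follow-up. Moving a censoring time later without information keeps the patient in the risk set for time in which a death would not have been seen, so the estimate can only rise.

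If a patient is contacted on the end date, the two sentences agree and the second adds nothing. It changes a result only when it credits unobserved time. The trial is open-label, so the choice between the sentences should not be left to programming after survival data are visible.

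**Working it through.** No sample size, power or event count in the documents depends on the OS censoring date, so there is no planned figure to reproduce. The check compares the two rules and then sizes the difference.

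**Step 1. Rules compared, by patient.**

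- Survival status documented on the end date: last contact is that date, so the rules agree.
- In regular follow-up, last contact up to about 60 days earlier: the second sentence adds up to 60/7 = 8.6 weeks, or 30/7 = 4.3 weeks on average if contacts are spread evenly.
- Out of contact for longer: it adds the whole gap, if the patient is treated as alive.

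**Step 2. Regular follow-up at the final Part C analysis.** With exponential survival the median is ln2 × (total follow-up) / deaths. A gap g added to each survivor therefore raises it by ln2 × (survivors/deaths) × g, whatever the median is. Inputs: 47 patients treated in Part C (Protocol 7.1). As an assumption, the 85% trigger is taken as the share of these 47 who have died: 0.85 × 47 ≈ 40 deaths and 7 survivors.

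- g = 4.3 weeks: 0.693 × 7/40 × 4.3 = 0.5 weeks.
- g = 8.6 weeks: 0.693 × 7/40 × 8.6 = 1.0 week.

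This applies to the parametric sensitivity analysis (Weibull without a shape parameter) in SAP 5.3.8.1. A Kaplan-Meier estimate changes only where a death falls between the two censoring dates, so mainly in the tail.

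**Step 3. Patients out of contact (loss rates assumed).** Kaplan-Meier simulation with 4,000 replicates. OS is exponential at the medians reported in Protocol 5.1.5.2: 31.4 weeks (Part A, n = 109) and 73.0 weeks (Part B, n = 40). Analysis is at 82 deaths (75% of 109, SAP 5.3.2) and 30 deaths (Protocol 7.1). Accrual of 78 and 52 weeks is assumed. A fraction p is assigned a loss time, uniform from 0 to twice the median. Each cell compares censoring at last contact with carrying the patient to the common analysis date.

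| p | Part A-like median (weeks) | Part B-like median (weeks) | Survival at twice the median, A | Same, B |
|---|---|---|---|---|
| 0 | 31.5, no change | 70.1, no change | 0.25, no change | 0.24, no change |
| 10% | 31.5 to 32.6 | 72.1 to 72.6 | 0.248 to 0.277 | 0.242 to 0.270 |
| 20% | 31.3 to 33.6 | 72.6 to 75.1 | 0.249 to 0.307 | 0.245 to 0.302 |
| 30% | 31.3 to 35.1 | 72.4 to 77.5 | 0.249 to 0.337 | 0.244 to 0.330 |

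Not everyone assigned a loss time is lost alive. The share is 0.75/(2 ln2) = 0.541, so p = 10% means at most about 5.4% out of contact while alive.

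**Step 4. Hand check.** In large samples, survival at twice the median under carrying forward is (1 − p) × 0.25 + p × 0.541. That gives 0.279 at p = 10% and 0.308 at p = 20%, in line with the table.

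For the median, write q = 2^(−x), with x in units of the true median, and solve (1 − p)q + p[(1 − q)/(2 ln2) + (1 − x/2)q] = 0.5. At p = 10%, x = 1.034, so 31.4 becomes 32.5 weeks and 73.0 becomes 75.5 weeks. The Part A-like simulation agrees. The smaller Part B-like shift (0.5 weeks) reflects the coarse steps of a Kaplan-Meier curve with 40 patients, so it is not an upper limit.

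Parts A and B serve here only because the protocol reports their medians. Their own cut-off analyses are not governed by the second sentence.

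**The case against.** Four stronger readings are tempting, and the documents do not support them.

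- **That the SAP replaces last-contact censoring.** It does not. The protocol's rule stands in the sentence immediately before. The defect is an unreconciled addition.
- **That Part A and B results are distorted.** About 10 of 40 Part B patients would be alive at 30 deaths, and a reader might count them all as affected. But those analyses are made at their own event-driven cut-offs, where the last-contact rule applies.
- **That survivors gain a year or more.** Carrying every survivor 52 weeks past last contact would lift exponential medians from 73.0 to 85.0 weeks (Part B) and from 31.4 to 43.3 (Part A). That needs an OS analysis at the trial-level end date, and none is specified. SAP 5.3.2 makes the Part C analysis the final one, and Protocol 7.1.1 puts extension data in an addendum listing. The words bringing extension patients into the end-of-study definition came with Amendment (e) in August 2016, after this SAP was approved in October 2013. Protocol 7.1.1 also allows later survival enquiries, so these patients are not necessarily beyond contact.
- **That patients lost to follow-up will be carried forward.** The two sentences can be read as contrasting unknown status with known alive, which would put lost patients under the first rule. SAP 5.3.4 says only that missing time-to-event data are censored, without a date.

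The bias also disappears if alive means confirmed alive on the end date, and largely disappears if the end of the study is the patient's own exit. OS is secondary, no formal powered efficacy test is planned, and the shifts at 10% are small beside the reported 95% intervals (22.9 to 40.6 weeks in Part A, 45.4 to 104.7 in Part B).

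All of this limits the size. It does not remove the conflict: the text leaves the choice open, and a literal study-level reading gives a biased rule.

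**Conclusion.** The point holds as a conflict within the SAP, with a conditional bias of known direction. The second sentence can act on the study's final OS analysis, that of Part C. There it adds up to about one contact interval per survivor in regular follow-up (0.5 to 1.0 week on an exponential median, taking 40 deaths in 47), and more for anyone out of contact who is treated as alive. It has no effect where status is documented on the end date.

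The figures for lost patients are illustrative: the documents give no loss rate, and the accrual periods and exponential shape are assumed. TTP, the primary endpoint, has its own censoring rule and is unaffected.

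**What to change.** Delete the second OS sentence from SAP 5.1.1, or limit it to patients whose survival status is documented on that date. Every patient without a recorded death is then censored at the last date known alive on or before the data cut-off, as in Protocol 12.2.2. Optionally, list the interval from last contact to cut-off for each censored patient, so that the completeness of OS follow-up can be judged.

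The cost is one sentence and, if wanted, one listing. Protocol 12.2.8 already calls for further SAP versions for Parts D and E, so the edit can go in with those. No sample size, event count or power changes. OS estimates may come out slightly less favourable.

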- Time to progressive disease is measured from the date of randomization to the first date of progression of disease. For each patient who is not known to have had a progression of disease as of the data-inclusion cut-off date for a particular analysis, or who has died without progression of disease, time to progressive disease will be censored for that analysis at the date of the patient's last tumor assessment prior to that cut-off date. Time to progressive disease will be calculated and analyzed twice: (1) including clinical progressions of disease not based on lesion measurements, and (2) excluding clinical progressions.
- Duration of tumor response is measured from the date of the first objective status assessment of a CR or PR to the first date of progression of disease or death from any cause. For each patient who is not known to have died or to have had a progression of disease as of the data-inclusion cut-off date for a particular analysis, duration of tumor response will be censored at the date of last prior contact.
- Time to treatment failure is measured from the date of randomization until the date of discontinuation of study treatment due to AE, progression of disease, or death from any cause. For each patient who has discontinued study treatment for any other reason, time to treatment failure will be censored at the date of discontinuation of study treatment. If a patient is still on study treatment as of the data-inclusion cut-off date for the particular analysis, time to treatment failure will be censored for that patient at that cut-off date.

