5.3.3. General Considerations

All patients who have received at least 1 dose of study drug will be evaluated for safety, efficacy, toxicity, and pharmacodynamic endpoints. The pharmacodynamic responses will focus on the AFP kinetics and the TGF- β 1 levels but also include the assessments of EMT associated markers (for example, E-cadherin) and fibrosis-related blood markers.

Patients with measurable disease will be included in summaries of tumor response. Tumor response will only be tabulated for patients who received at least 1 dose of study drug and have measurable disease at baseline.

After Amendment (b), patients are allowed to continue on study treatment at the investigator's discretion, even when objective progression is determined by radiological measurements, if they do not have overall symptomatic deterioration as well. This change should not affect the primary objective (estimation of TTP), PFS, or response rate. However, bias may be introduced in the assessment of OS, since patients prior to Amendment (b) will have discontinued based on objective progression alone. Therefore, patients discontinued from objective progression prior to the amendment (b) will be considered separately from those that discontinued due to objective progression or overall symptomatic deterioration after the amendment in the assessment of OS.

Patients from all sites will be pooled for all analyses. All tests of treatment effects will be conducted at a 2-sided alpha level of 0.10, unless otherwise stated. Patients with Child-Pugh Class A and B7 will be considered as 1 group of patients, given the similarity of Class B7 patients to Class A patients. If all patients in Part A and Part B are second-line, Part C patients will be analyzed as a separate group. If there are some first-line patients in Part A or Part B, different subgroups may be considered.

Efficacy:

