5.3.8. Efficacy Analyses

5.3.8.1. Clinical Efficacy Analyses

Time to tumor progression (TTP) is the primary clinical endpoint for this study. A listing of TTP, including date of first dose, date of progression, date of death, censoring and TTP duration will be listed. The time to progression distribution will be characterized using the Kaplan-Meier method. Kaplan-Meier curves of TTP will be presented. Median TTP, quartiles and TTP rate after specific time points (for example, after 12 months and 24 months on treatment) will be estimated from the survival curves. All these parameter estimates will be reported together with their 90% confidence intervals. A comparison between the observed TTP distributions of each dose cohort will be performed using the log rank test and the p-value reported. The hazard ratio between the observed TTP distributions of different cohorts/parts (or different subgroups of interest) will be estimated. The interpretation of any estimate will be considered in light of the size of this subgroup. The list of possible comparisons are:

- 1) In part A: 160 vs 300 mg (160 reference)
- 2) Between Part A and Part B 300 mg groups (Part A reference)
- 3) Between Part A, Part B and Part C (sorafenib naïve or not)

Sensitivity analyses using alternative distributions of survival times, such as Weibull (with and without estimating a shape parameter) will be explored and median TTP with its 90% CIs will be reported.

Secondary time-to-event parameters will follow the same analyses described above.

Additional exploratory analyses on clinical endpoints such as TTP or OS will be carried out. Prognostic factors, such as baseline AFP levels, etiology, and whether sorafenib naïve or not, may be added to the time-to-event models to explain the variability in duration of progression. Analyses using subgroup identification methods, such as classification and regression tree (CART) (classification and regression tool) may also be carried out.

The best overall response rate and clinical benefit rate together with their 90% exact confidence intervals will be reported for each dose cohort in Part A, Part B and Part C. These rates will be compared between dose cohorts using Chi-squared tests. Odds ratios, 90% confidence intervals and p-values will be reported. Cohorts comparison should follow the above list for types of comparisons for TTP and OS.

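### Time to treatment failure (TTF) runs to stopping of drug, and Amendment (b) allows treatment past progression, so TTF contrasts by dose and by part tilt towards patients enrolled later; the SAP guards only OS

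*SAP*

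**What the plan says.** SAP 5.1.1 lists TTF as a secondary efficacy endpoint. It "is measured from the date of first dose until the date of discontinuation of study treatment due to AE, progression of disease, or death"; the clock stops when the drug stops, not when the tumour progresses. Stops for other reasons are censored: "For each patient who has discontinued study treatment for any other reason, time to treatment failure will be censored at the date of discontinuation". Protocol 12.2.2 has the same structure ("Time to treatment failure is measured from the date of randomization until the date of discontinuation of study treatment due to AE"), differing in its start date.

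The stopping rule changed during the trial: "From Amendment (b), patients that are clinically asymptomatic may continue on study treatment even if they have objective progression". Of those who continue, the SAP says: "These patients will then be discontinued from study treatment because of overall symptomatic deterioration, worsening of biomarker results, or other causes".

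The SAP protects some endpoints from this change. In 5.1.1: "The time to tumor progression, progression free survival, and response rate will be estimated up to the date of objective progressive disease". In 5.3.3: "This change should not affect the primary objective (estimation of TTP), PFS, or response rate". That section then warns of possible bias in OS and has patients who stopped before and after the amendment considered separately for OS. Protocol 12.2.1 also names OS alone. Neither document mentions TTF in this context.

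SAP 5.3.8.1 gives TTP Kaplan-Meier estimates, a log-rank p-value and HRs with 160 mg v 300 mg in Part A and Part A v Part B at 300 mg among the comparisons. It adds: "Secondary time-to-event parameters will follow the same analyses described above". That includes TTF.

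**The concern.** TTF is the endpoint that the amendment changes most directly, because its end date is the treatment-stop date that the amendment altered. There are two routes.

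1. **Later end date.** A patient who progresses without symptoms and continues has a TTF that runs past progression. Before the amendment, the same patient would have stopped at progression.
2. **Lost event.** If that patient later stops for worsening biomarkers or another cause, the stop may be recorded as neither adverse event, progression nor death. It is then censored, although progression was documented. This route depends on how the stop is coded.

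The groups being compared were not equally exposed to the new rule. A contrast between them therefore partly measures the change in the rule. For 160 v 300 mg, that could be read as a dose effect. Recommending doses for future trials is a secondary objective.

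**Working it through.** The documents give no figure for TTF, so there is none to reproduce.

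**Exposure by enrolment**
- Protocol 5.1.7: 74 patients were randomized when the 160 mg arm was dropped. Protocol 12.1: final sizes 37 (160 mg) and 72 (300 mg).
- 300 mg patients already enrolled: 74 − 37 = 37. Enrolled later: 72 − 37 = 35, and 35/72 = 49%.
- Part B was opened by Amendment (b) (Protocol 7.1), so 40 of 40.
- 160 mg patients enrolled later: 0 of 37.

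**Model with no drug effect**
- Time to progression T is exponential with median 3 months in every group (the reference median in Protocol 12.1). Its mean is 3/ln 2 = 4.33 months.
- Among patients under the new rule, a share q of progressors continue for an exponential extra time of mean d months. A share c of these are censored when they stop. The documents give none of q, d or c.
- Mean TTF = 4.33 + s·q·d, where s is the share of the group under the rule: 0 (160 mg), 0.49 (Part A 300 mg), 1 (Part B).

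For q = 40%, d = 2, c = 0:
- Part A 300 mg: 4.33 + 0.486 × 0.4 × 2 = 4.72.
- Part B: 4.33 + 1 × 0.4 × 2 = 5.13.
- Ratios of means: 4.33/4.72 = 0.92 and 4.72/5.13 = 0.92.

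Cox models on simulated data from the same model:

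| q, d (months) | c | HR 300 v 160 mg | HR Part B v Part A 300 mg |
|---|---|---|---|
| 20%, 1 | 0 | 0.98 | 0.98 |
| 40%, 2 | 0 | 0.92 | 0.91 |
| 60%, 3 | 0 | 0.83 | 0.84 |
| 40%, 2 | 30% | 0.86 | 0.86 |

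In the second row, median TTF is 3.0, 3.4 and 3.9 months for 160 mg, Part A 300 mg and Part B.

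**Allowing for 160 mg patients who could use the rule.** If 15% to 30% of earlier patients in both doses had access, the 0.92 becomes 0.93 to 0.94.

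**At the trial's own sample sizes.** Take 37 v 72 patients, with median time to progression 11.9 weeks (the Part A result in Protocol 5.1.5.2). Assign the rule by date of progression, with an assumed 70 weeks of accrual before the amendment, and count later stops as events:
- Half continuing for a mean of 8 weeks: HR 0.90 to 0.92 over repeated runs. The 90% CI wrongly favours 300 mg in 11% to 13% of trials, against a nominal 5%.
- 30% continuing for 6 weeks: HR 0.95, 8%.
- 20% continuing for 4 weeks: HR 0.98, 6.5%.

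**If half of the later stops are censored** (half continuing for 8 weeks): HR 0.78 to 0.81 with the rule assigned by enrolment, and 0.83 if a quarter of earlier patients also had access.

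**After the fix.** With TTF ended at objective progression, the no-effect HR is 1.00.

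**The case against.** The strongest reply is that the effect is modest and little depends on it.

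- **Who was exposed.** Protocol 5.1.7 applies the rule to all patients, and Protocol 7.1 keeps 160 mg patients still on treatment at their dose. What matters is when a patient progressed, not when the patient enrolled. This stands: it dilutes the contrast but leaves its direction.
- **How stops are coded.** Protocol 8.3.1 places clinical symptoms inside the progressive-disease criterion, so a stop for symptomatic deterioration would naturally count as progression. This also stands. A reader might infer a very large bias: if every later stop were censored, with half continuing for 8 weeks and no exposure at 160 mg, the HR would be 0.71 and 48% of trials would falsely favour 300 mg. The documents do not support that coding.
- **What Part A v Part B means.** A reader might infer that the artefact would look like a drug effect there too. It would not: drug, dose and schedule are the same, and the groups are defined by AFP. The distortion concerns AFP groups.
- **Consequence.** TTF is not named in the objectives, no interim rule uses it, and the 160 mg arm was closed before Amendment (b). Efficacy comparisons are for estimation without powered testing. All of this limits importance. SAP 5.3.8.1 nevertheless reports p-values and HRs for TTF.

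The planned baseline comparison of earlier and later 300 mg patients (SAP 5.3.6.1) concerns prognosis and does not address this bias.

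**Conclusion.** The omission is real and the direction is clear: towards 300 mg in 160 v 300 mg, and towards Part B in Part A v Part B. With later stops counted as events, the spurious 300 v 160 mg HR is about 0.90 to 0.98. It is lower, about 0.8, if half of those stops are censored, and 0.83 even without censoring if 60% continue for a mean of 3 months and no 160 mg patient had access.

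These sizes rest on assumed continuation shares, durations and coding. The 35/72 split assumes that the new rule began when the 160 mg arm was dropped; the amendment's start at each site is not given, and Protocol 12.1 counts 64 treated patients at that review, against 74 randomized.

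A reader might infer that the primary result is compromised. It is not by this route: TTP and PFS are tied to objective progression. The point should be corrected, but it does not threaten the main conclusions.

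**What to change.** **Preferred.** In SAP 5.1.1, end TTF for all patients at the earliest of objective progression, death, or stopping for an adverse event or progression, stating that stops for symptomatic deterioration count as progression. SAP 5.1.1 says the dates of objective progression and symptomatic deterioration are on the CRF. Report time on treatment separately and descriptively, without between-group tests.

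**Minimum.** Add TTF to the bias statement in SAP 5.3.3 and extend to it the pre/post-Amendment (b) separation planned for OS. Protocol 12.2.1 already asks that patients enrolled under each amendment be identified.

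**Cost.** A changed definition and a re-derivation from existing data. Protocol 5.1.5.2 reports Parts A and B as completed, so for them this is a re-analysis; Protocol 12.2.1 lets non-principal analysis changes be justified in the study report. The downside is that the redefined TTF comes close to PFS plus adverse-event stops. The minimum option keeps TTF as a measure of time on treatment, but with smaller groups in each comparison.
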